
General Overview:

This within-subjects study will examine the effects of daily repeated use of cannabis on pain and its relationship to abuse liability. Healthy, non-treatment seeking cannabis smokers (N=16, 8M, 8F) will be admitted to the research center on 5- South of NYSPI for a 16-day inpatient stay. On the first full inpatient day, participants will smoke active cannabis (4.91% CBD/2.98% THC). Days 2-8 will comprise the Inactive Phase, in which placebo cannabis (0% CBD/THC) will be administered 3x/day. The next 7 days (Day 9-15) will be the Active Phase, in which active cannabis (4.91% CBD/2.98% THC) will be administered at the same time points (Table 1). Participants will complete subjective effects visual analog scales and a cannabis rating form daily, and will complete the Cold-Pressor Test and Quantitative Sensory Testing-Thermal Temporal Summation on Days 1, 2, 5, 8, 9, 12, and 15 to explore three critical questions regarding cannabis' therapeutic utility for pain (as illustrated in Figure 1): 1) If abruptly switching active cannabis to inactive cannabis increases experimental pain sensitivity, i.e. hyperalgesia (Day 2-8; red bars) relative to baseline and if these effects parallel measures of cannabis withdrawal such as disrupted mood and sleep; 2) If pharmacological tolerance to the analgesic and abuse-related effects of cannabis is reversed following 7 days of abstinence from active-THC cannabis (by administering 0% CBD/THC, inactive cannabis): defined as a) a significant decrease in CPT latencies and QST-TTS response following active cannabis administration on Day 12 or Day 15 compared to Day 9 (Active Phase), and b) a significant decrease in subjective visual analog scale ratings of abuse, i.e. 'Good Drug Effect' following active cannabis administration on Day 12 or Day 15 (Active Phase) compared to Day 9 (Active Phase); 3) If tolerance is present/develops to repeated, daily smoked cannabis (4.91% CBD/2.98% THC) administration on measures of experimental pain and abuse liability (green bar): defined as a significant increase in CPT latencies and QST-TTS response and 'good drug effect' after active cannabis administration when Day 9 of the Active Phase is compared to Day 1.

Provide the hypothesis for this research.

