- 1) The Cold Pressor Test (CPT) is a validated and reliable pain-induction procedure that reflects A-delta nerve fiber activity within the autonomic nervous system and closely mimics clinical chronic pain. CPT has been shown to have excellent reliability and predictive validity for medication-induced analgesia, including cannabinoids. For this task, two temperature- controlled circulating water baths maintain warm (36.5-37.5°C) and cold (3.5-4.5°C) water. Participants immerse their hand into a warm bath for 3 min (to standardize baseline skin temperature), then the cold bath, indicating when they first experience pain and withdrawing when the pain gets uncomfortable. Study staff will record time (in seconds) until participants: 1) report discomfort (pain threshold), and 2) withdraw their hand from the cold water (pain tolerance): 15 min.
- 2) Quantitative Sensory Testing-Thermal Temporal Summation (QST-TTS) uses repetitive fixed frequency and intensity heat stimulation to induce central sensitization of C-fibers in the spinal cord and is regarded as an experimental correlate of the 'wind-up' phenomenon in the dorsal horn. As dorsal horn CB-1 activity has been linked to suppression of 'wind-up' and central sensitization (the mechanism purportedly underlying cannabis' efficacy for neuropathic pain), cannabis use may decrease QST-TTS response, mirroring analgesia on the CPT during active cannabis administration vs. placebo. For this task, a Medoc TSA-II NeuroSensory Analyzer with a 30 x 30 mm Peltier thermode applies tonic noxious heat stimulation to the thenar eminence of the palm: the baseline temperature is 32.0°C, increases at a rate of 1°C/s up to 46.5°C, and remains constant for 120 sec. Total duration: 3 min.
- 3) Cold Pressor Test Visual Analog Scale (CPT-VAS): 11-item questionnaire rating the physiological and subjective effects of the cold water on a 100 mm VAS after the CPT: 15 sec.
- 4) Quantitative Sensory Testing-Thermal Temporal Summation Computerized Visual Analog Scale (CoVAS): Participants rate magnitude of perceived pain on a 100 mm VAS during the QST-TTS: 135 sec.
- 5) Physiological response to pain: Heart rate and blood pressure will be measured throughout pain assessments: 2 min.
- 6) Pain Intensity/Bothersomeness Scale (PIBS): Ratings of CPT and QST pain on a 0-to-10 scale: 0 being 'not painful/bothersome at all' and 10 being 'most painful/bothersome feeling imaginable': 10 sec.

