- 7) Subjective Effects: A series of 100 mm VAS in which participants indicate how they are feeling at that

moment will be completed 3x/day. The 44-item VAS includes mood, physical symptom, and drug effect descriptors. Based on a cluster analysis, we employed arithmetic means of individual item scores to reduce 34 of the 44 items into eight subscales: good drug effect; miserable; irritable; anxious; bad effect; social; and confused. We also analyze individual VAS drug craving ratings. These subjective measures may detect changes in abuse-related effects as well as changes in mood (miserable, irritable, anxious, cannabis craving) as a function of cannabis condition: 3 min.

8) Objective Sleep Measures: Participants will wear an Actiwatch Activity Monitoring System that tracks gross motor activity (Actiwatch®: Respiromics Company, Bend, OR) and records objective sleep outcomes (hours slept, number of awakenings). We have used this system effectively to demonstrate perturbations in sleep as a function of cannabis withdrawal.

9) Sleep Questionnaire: Participants will complete a sleep questionnaire which consists of a 7-item, 100 mm VAS instrument that assesses the quality of sleep and how many hours slept the previous night and wakefulness in the morning. Participants will be asked to rate symptoms by placing a mark on a line representing a continuum from "not at all" (on the left of the line) to "extremely" (on the right of the line) indicating how the phrase relates to the last night's sleep: 30 sec.

10) Cannabis Rating Form (CRF): Participants rate the strength, liking, desire to take again, good drug effect and bad drug effect of cannabis on a 100mm VAS: 2 min.

Please attach all Questionnaires and Assessments listed above.
No answer provided.

Describe the procedures in sufficient detail so that a reviewer, who is not familiar with them, can comprehend what is to be done and can evaluate any risks.

This study is now in data analysis only, and the following procedures describe the study as it was approved and conducted during the COVID era.

Consent Procedures:

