Title: Repeated Cannabis Administration on Experimental Pain and Abuse Liability

NCT: 04576507

Document date: April 14, 2025

Statistical Analysis

Overview: All data analyses will be based on models using repeated measures analysis of variance (RM-ANOVA) analyzed as a function of cannabis condition (active vs. inactive) and day (Day 1-15), and sets of planned comparisons, calculated with SPSS or SUPERANOVA statistical packages. The planned comparisons are *a priori*, and designed to test the specific hypothesis for each aim. Tests of differences for all comparisons will be based on F-statistics with degrees of freedom corrected, depending on the observed within-subject correlation of the measures, using the method of Geiser and Greenhouse or Huynh and Feldt. Results will be considered statistically significant at $p < 0.05$, using 2-tailed tests. Distribution of demographic variables (ethnicity, age, sex) will be described in terms of means, standard deviations, proportions, and 95% confidence intervals, where appropriate.

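### Tolerance is defined by a joint criterion across several measures, which costs power, cannot support an analgesic-only conclusion, and fixes one direction for outcomes that should move oppositely

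*Protocol*

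**What the plan says.** In the protocol's General Overview, question 2 is answered by two lettered parts. Part (a) is "a significant decrease in CPT latencies and QST-TTS response following active cannabis administration", and part (b) is a significant fall in subjective VAS ratings of Good Drug Effect. Both are assessed "on Day 12 or Day 15 compared to Day 9 (Active Phase". Question 3, on the single contrast of Day 9 with Day 1, requires "a significant increase in CPT latencies and QST-TTS response and 'good drug effect' after active cannabis administration".

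Under Experimental Assessments, the CPT yields two latencies, the times until participants "1) report discomfort (pain threshold), and 2) withdraw their hand from the cold water (pain tolerance". QST-TTS yields a continuous pain rating with no named summary. 'Good drug effect' appears in two instruments. One is a subscale of the 44-item Subjective Effects VAS, listed among "eight subscales: good drug effect; miserable; irritable; anxious; bad effect; social; and confused". The other is an item of the Cannabis Rating Form, on which "Participants rate the strength, liking, desire to take again, good drug effect and bad drug effect of cannabis on a 100mm VAS".

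The protocol's Statistical/Data Analysis Plan and the SAP Overview apply p<0.05 to every comparison, "using 2-tailed tests". Neither names a deciding measure, says whether all or any must be significant, or adjusts for multiplicity. The protocol announces a list of planned comparisons, but none follows, and the SAP has none. The sample-size justification gives alpha 0.05, d=0.7, within-subject correlation 0.6 and 20 completers out of 24 enrolled, with no target power.

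**The concern.** A conclusion of tolerance depends on how the word 'and' is applied to three or more p-values. If all must be significant, the chance of success is below that of the single-outcome calculation behind n=20. If one is enough, 0.05 is no longer the error rate. The documents do not choose, and the study procedures section says the study is now in data analysis only (the SAP is dated April 14, 2025), so an unwritten choice will be made with data in hand.

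Two further problems do not depend on arithmetic. First, Aim 2(a) hypothesises reversal of analgesic tolerance alone, but the question 3 rule, which holds the matching contrast, also demands a change in 'good drug effect'. A clear analgesic result with a flat subjective rating would fail it. Aim 2(b) predicts tolerance to analgesic but not abuse-related effects, so if parts (a) and (b) of question 2 are both required, the rule is met only when that hypothesis is wrong. Second, the rule gives CPT latency and QST-TTS response the same direction.

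**Working it through.** **Inputs from the protocol's sample-size justification.** n=20 completers, d=0.7, r=0.6, two-sided alpha 0.05. The dropout step reproduces: 20/(1 − 4/24) = 24. The power behind n=20 cannot be reproduced because none is stated.

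**Assumption.** The documents give no correlation between the change scores of different measures. I use 0.3 to 0.7, with independence as a bound. The same true effect is assumed on every measure.

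**One measure, one contrast (paired t, 19 df, exact noncentral t).**
- If d is scaled by the raw SD: dz = 0.7/√(2(1 − 0.6)) = 0.7/√0.8 = 0.783. Noncentrality is 0.783 × √20 = 3.50; power 91.3%.
- If d is already dz = 0.7: noncentrality is 0.7 × √20 = 3.13; power 84.4%.

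**All measures required, Day 9 against Day 1, n=20.** Correlated paired t tests were simulated; repeat runs differ by up to about one point.

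| Rule | dz = 0.783 | dz = 0.7 |
|---|---|---|
| One measure | 91% | 84% |
| Three pain measures, correlation 0.3 to 0.7 | 78% to 83% | 64% to 72% |
| Same, independent (0.913³; 0.844³) | 76% | 60% |
| Three pain measures plus good drug effect, correlation 0.3 to 0.7 | 73% to 80% | 57% to 68% |

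The General Overview gives N=16 instead of 20. At 16 and dz = 0.783, the three-measure figure is 62% to 70%, against 83% for one measure.

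**Any one of three pain measures sufficient, no true effect, n=20.**
- Independent, two-sided: 1 − 0.95³ = 14.3%. In the predicted direction: 1 − 0.975³ = 7.3%.
- Correlation 0.3 to 0.7: about 11% to 14% two-sided against 5%, and about 5.5% to 7% in the predicted direction against 2.5%.
- Correlation 0.8 and 0.9: 10.0% and 8.4% two-sided, so the rate is no longer more than double at about 0.8 and above.

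**Either of two Good Drug Effect instruments.** At most 1 − 0.95² = 9.75% two-sided, or 1.95 times 5%.

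**Question 2, all three pain measures, each on either day.** With the effect present on both days and an assumed correlation of 0.5 between the two day contrasts, power at n=20 is 83.5% to 90.2% (dz = 0.7) or 92.7% to 95.5% (dz = 0.783), for correlations between measures of 0 to 0.9. That is essentially no loss against one measure on one contrast.

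**Direction, by comparing sections.** Experimental Assessments, item 2, says cannabis may lower QST-TTS response as the counterpart of CPT analgesia. Aim 1 likewise treats a higher QST-TTS response as hyperalgesia. Loss of analgesia should then shorten CPT latency and raise QST-TTS response. Question 2 requires both to fall, and question 3 requires both to rise. If item 2 is right, a true effect of the assumed size on every measure would almost never satisfy either joint rule, and the power figures above do not apply.

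**The case against.** The literal wording is 'and', and a conjunction does not inflate error: with all three pain measures required on one contrast, the false-claim rate in the predicted direction is below 0.5% at correlations of 0.3 to 0.7. The any-of-three reading arises only because no rule is stated. The study is also a pilot that sets out to explore its questions. All of this stands, and it limits the seriousness of the point. It does not remove it, because both documents call the comparisons a priori and hypothesis-testing, and the literal reading is the one that loses power and conflicts with Aim 2.

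A reader might infer more than the documents support:
- **That the error rate more than doubles for Good Drug Effect.** Two instruments alone cannot reach double. The General Overview also lists the subjective-effects VAS separately from the Cannabis Rating Form and words the question 2 criterion in terms of subjective VAS ratings, which points to the 44-item instrument.
- **That power falls below the planned level.** No planned level is stated. Had 80% been intended, 78% to 83% would be close to it.
- **That question 2 loses power.** Its either-day rule largely restores it when the effect is present on both days. The loss belongs mainly to question 3.
- **That CPT hand-withdrawal latency should be the sole deciding measure.** No section ranks it above threshold or QST-TTS, and choosing it now would itself be a choice made with data in hand.

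**Conclusion.** The concern holds in this form: the tolerance criteria join at least three pain measures, and in question 3 a fourth outcome, without an operative decision rule. For question 3 read literally, power is about 8 to 13 points below that of a single measure at dz = 0.783, or about 12 to 20 points at dz = 0.7, and lower again with good drug effect included. Read as any of three, the false-claim rate in the predicted direction is about 5.5% to 7% instead of 2.5%. These sizes rest on n=20, equal true effects, and correlations between measures that are assumed and not documented.

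The mismatch with Aim 2 and the conflict over QST-TTS direction rest on the text alone and are the firmer grounds for change. This should be corrected before results are reported; it does not invalidate the study.

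**What to change.** In the SAP, and in the General Overview definitions:

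1. Delete the joint criterion. Give CPT threshold, CPT tolerance and QST-TTS response separate conclusions, with Holm adjustment across these three within each question. The count of three presumes one stated summary per measure, including which QST-TTS summary and which post-dose times count.
2. State for each measure the direction that indicates loss of analgesia, reconciling the General Overview with Experimental Assessments, item 2.
3. Judge abuse liability separately on the Good Drug Effect subscale of the 44-item VAS, with the Cannabis Rating Form item supportive.
4. Label these choices as made during data analysis.

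The cost is a few sentences and slightly stricter thresholds for the pain measures. Holm's first step is 0.05/3 = 0.0167, at which power per measure at n=20 is 79.9% (dz = 0.783) or 69.1% (dz = 0.7). These are floors, because later Holm steps are less strict. The Day 12 or Day 15 alternative in question 2 is a separate source of multiplicity that this change does not address.

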Aim 1. Determine the effects of abstinence from active cannabis (by use of 0% THC cannabis) on experimental pain. We hypothesize that (a) abrupt abstinence will result in increased CPT and QST-TTS responses, indicative of withdrawal-induced hyperalgesia.

Aim 2. Determine if a) tolerance is present (Day 1) and is reversed following abstinence from active cannabis (Days 2-8); b) tolerance develops to daily smoked active cannabis (4.91% CBD/2.98% THC; Days 9-15) administration on pain and abuse liability measures. We hypothesize that: (a) existing analgesic tolerance will be reversed following abstinence from active cannabis; (b) over the course of the active cannabis phase, tolerance will develop to cannabis' analgesic but not abuse-related effects.

Include pertinent information about the relationship of the proposed research to previous studies and describe the significance of the proposed research. Be brief.

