Since we will recruit moderate-heavy cannabis users with varied use patterns, they will enter the study with varying pharmacological tolerance. Therefore, Study Day 1 will be an initial day of active cannabis administration to standardize exposure to the same strength of smoked cannabis across participants prior to enforced abstinence from active cannabis in the Inactive Phase (Day 2-8). Participants will be administered active cannabis (two one 4.91% CBD/2.98% THC cigarettes) at 1000h, 1300h, and 1600h.

Days 2-8 (Inactive Phase)

On Study Days 2-8, participants will be administered one inactive cannabis cigarette (0.00% CBD/THC) at the same three time-points (1000, 1300, 1600). We have shown that inactive cannabis controls for expectancy effects of smoking, producing small but reliable increases in ratings of 'high' [5]. Therefore, this phase will assess how abstinence from active- THC cannabis affects pain outcomes in parallel to measures of cannabis intoxication and withdrawal (mood, sleep).

Days 9-15 (Active Phase)

On Study Days 9-15 participants will be administered an active cannabis cigarette (one 4.91% CBD/2.98% THC cigarette) at the same three time-points (1000, 1300, 1600), with the exception of Day 15 where they will be administered active cannabis only at 1000. This phase will allow us to see if CPT and QST pain outcomes and abuse liability change over time

Move Out

Following completion of all assessments of Day 15, the PI will discuss with the participants benefits of cannabis cessation, highlighting availability of a range of treatment options, prior to discharge. At 180 minutes post-cannabis administration, participants will complete field sobriety tests, vital signs, and a Mini-Mental State Exam (MMSE), and will be permitted to leave once they meet discharge criteria. Criteria for discharge will be met when participants report no ongoing subjective drug effects and have no signs of impairment or intoxication, pass the field sobriety test, have normal vitals, and a normal mental status score as assessed by the MMSE. [name], [name], or [name] will make the final determination that the patient is sober and medically stable and can leave the facility.

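### Aim 2(a): the only written contrast that uses Day 1 shows tolerance as present only if seven days reverse it, so a null Day 9 v Day 1 result cannot mean that tolerance was absent

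*Protocol*

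**What the plan says.** The protocol's hypothesis section sets Aim 2(a): "Determine if a) tolerance is present (Day 1) and is reversed following abstinence from active cannabis (Days 2-8"). That is two questions, one about Day 1 and one about the Inactive Phase. The matching hypothesis covers only the second, that "existing analgesic tolerance will be reversed following abstinence from active cannabis".

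The General Overview gives the working definitions.

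- **Item 2** asks "If pharmacological tolerance to the analgesic and abuse-related effects of cannabis is reversed following 7 days of abstinence from active-THC cannabis". For pain it is defined as "a significant decrease in CPT latencies and QST-TTS response following active cannabis administration on Day 12 or Day 15 compared to Day 9 (Active Phase"), with a parallel definition for the abuse-related rating.
- **Item 3** asks whether tolerance is present or develops. It is defined as a significant increase "after active cannabis administration when Day 9 of the Active Phase is compared to Day 1".

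The Day 1 (Standardization) section says of participants that "they will enter the study with varying pharmacological tolerance". There is one subject group, heavy cannabis smokers. The protocol's Statistical/Data Analysis Plan announces planned comparisons but lists none, and the SAP lists none either. No other test of tolerance on Day 1 is written.

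**The concern.** To show that people are tolerant on Day 1, their response must be compared with a less tolerant one. The design has no low-tolerance group, so the only candidate is the same people on Day 9. Day 9 serves only to the extent that seven days of inactive cannabis have undone the tolerance. The test for presence is therefore a test for presence and reversal together.

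A non-significant result fits two quite different situations: no tolerance at entry, or tolerance that a week without active cannabis does not undo. The protocol's background section says it is unknown whether analgesic tolerance can be reversed by abstinence, so the second is a live possibility. The two mean very different things for the daily users whom the study wants to inform.

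The definition attached to reversal does not help. Day 12 or Day 15 v Day 9 lies wholly within the Active Phase.

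**Working it through.** **1. What each contrast can show**

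| General Overview item | Label | Contrast | Period spanned | Part of Aim 2 it fits |
|---|---|---|---|---|
| 2 | reversed | Day 12 or 15 below Day 9 | Active Phase | 2(b), development |
| 3 | present/develops | Day 9 above Day 1 | Inactive Phase | 2(a), reversal |

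The two definitions appear interchanged relative to Aim 2.

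**2. Inputs**

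From the sample size justification: two-sided alpha 0.05, d = 0.7, within-subject correlation 0.6, 20 completers. N = 16 comes from the purpose section and the General Overview. The documents give no size for entry tolerance; 0.7 SD is my assumption, borrowed from the planning value. They also do not say how d is scaled, so I show both readings:

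- d on the raw SD: d_z = 0.7 / √(2 × (1 − 0.6)) = 0.783
- d already on the paired difference: d_z = 0.7

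**3. The plan's own figure**

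The protocol states no target power. A paired t-test with n = 20 has 91% power at d_z = 0.783 and 84% at d_z = 0.7. With n = 16 the figures are 83% and 74%. These apply to the tolerance question only if the whole effect is reversed.

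**4. Probability that true entry tolerance fails the definition of present**

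Let f be the fraction reversed by Day 9. The noncentrality is f × d_z × √n, and the definition is met if t exceeds its upper 2.5% point. Example, f = 0.5, n = 20, d_z = 0.783: noncentrality 0.5 × 0.783 × 4.472 = 1.75, critical value 2.093, probability met 0.383, probability missed 0.617.

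| Fraction reversed | n = 20, d_z 0.783 | n = 20, d_z 0.7 | n = 16, d_z 0.783 | n = 16, d_z 0.7 |
|---|---|---|---|---|
| 100% | 8.7% | 15.6% | 16.7% | 25.5% |
| 75% | 29.8% | 39.4% | 40.7% | 49.8% |
| 50% | 61.7% | 68.2% | 68.9% | 74.2% |
| 25% | 87.0% | 88.8% | 89.0% | 90.4% |
| 0% | 97.5% | 97.5% | 97.5% | 97.5% |

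The last row does not depend on the 0.7. With no reversal the expected difference is zero however large the tolerance, and only the 2.5% chance of a false rise remains. All figures are for one outcome.

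**5. Both written contrasts under different truths**

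Simulation with n = 20, correlation 0.6, full effect 0.7 SD, 20,000 runs:

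| Truth | Item 3 (present) met | Item 2 (reversed, as written) met |
|---|---|---|
| No entry tolerance, none develops | 2.5% | 4.6% |
| Entry tolerance, not reversed | 2.5% | 4.5% |
| Entry tolerance, reversed, redevelops | 91% | 97% |
| Entry tolerance, reversed, does not redevelop | 92% | 4.5% |
| No entry tolerance, develops in Active Phase | 2.4% | 98% |

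The first two rows cannot be told apart by either contrast. The last two show that item 2, as written, misses true reversal and is met where there was nothing to reverse.

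**The case against.** **Both questions rest on Day 9 v Day 1.** A reader might infer this, but the text does not say it. Item 2 assigns reversal to Day 12 or Day 15 v Day 9. Both parts of 2(a) fall on Day 9 v Day 1 only once the definitions are matched to the aim.

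**A null would be reported as tolerance not present.** This too is an inference. The General Overview says what counts as positive evidence; neither document says how a null is reported. The exact statement is that unreversed tolerance fails the protocol's definition of present. That stands, and nothing in the plan guards against the misreading.

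**Entry tolerance is presupposed.** The hypothesis concerns reversal, and a positive Day 9 v Day 1 result can support present and reversed jointly. This limits the harm to the negative reading. But the aim does ask whether tolerance is present, and item 3 offers a definition for it.

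**The percentages are mostly assumption.** This is fair for the rows between full and no reversal: both the fractions and the 0.7 SD are assumed. It does not touch the zero-reversal row.

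**The two contrasts could be read jointly.** It is tempting to say that if Day 9 is similar to Day 1 and the response later falls, Day 1 was not fully tolerant. But similar has no margin, and treating a non-significant difference as equality repeats the mistake. Take entry tolerance half reversed (Day 1 fully tolerant, Day 9 higher by 0.35 SD, correlation 0.6). With n = 20 such a rule wrongly calls Day 1 not fully tolerant in about 18% of trials if the response is halfway back by Day 12 and fully back by Day 15, and in about 26% if it is back by Day 12. With n = 16 the figures are about 17% and 24%.

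**Day 1 data alone could show presence.** A pre- to post-cannabis change on Day 1, or Day 1 against the inactive days, would show a drug effect. Without a low-tolerance reference it would not establish tolerance.

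**Conclusion.** The point holds as a limit on what a null result can mean, together with a mismatch between the General Overview definitions and Aim 2. Tolerance that seven days do not reverse fails the definition of present in 97.5% of trials, whatever its size. With an assumed 0.7 SD half reversed, it fails in 62% to 68% of trials at n = 20 and 69% to 74% at n = 16; the ranges reflect the two readings of d. The calculation assumes a paired t-test on a single outcome.

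A positive result is not free of doubt either. Phase order is fixed and the pain tests are repeated, so a Day 9 rise is consistent with tolerance present and at least partly reversed but does not prove it. The Day 1 reference is itself unclear: the Day 1 (Standardization) section gives both two and one as the number of cigarettes, while the Cannabis Administration section gives one per time point.

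**What to change.** - Match the General Overview definitions to Aim 2: Day 9 v Day 1 as the test of reversible tolerance (2a), and Day 12 or Day 15 v Day 9 as the test of development (2b). List both in the SAP as planned comparisons.
- Restate Aim 2(a) as one question: do seven days without active cannabis increase its acute effect?
- Report Day 9 v Day 1 with a 95% CI.
- State in the SAP that a null result means tolerance absent, or not reversed in seven days, and is not evidence that tolerance was not present. Add no rule that treats a non-significant difference as similarity.
- Describe a Day 9 increase as consistent with tolerance present and at least partly reversed, subject to fixed phase order and repeated testing.
- Reconcile the Day 1 (Standardization) and Cannabis Administration sections on the number of cigarettes on Day 1.

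The cost is wording in the protocol and SAP and a narrower aim. No new data are needed, so the change is still open although the protocol describes the study as in data analysis only.
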